9.7 DATA ANALYSIS

9.7.1 Main analysis

For all analyses, variables will be reported as follows:

- Continuous variables (e.g., age) will be presented as means (with standard deviation, SD) and/or medians (with interquartile range, IQR), minimum, maximum.
- Categorical variables (e.g., sex) will be presented as absolute and relative frequencies.

9.7.1.1 Descriptive Analysis

All variables specified in [section 9.3.3](#) will be reported. For demographic and lifestyle variables, the value recorded on the cohort entry date will be reported, otherwise the most recent known value will be reported. Presence of comorbidities and use of concomitant medication use will be determined based on whether they ever occurred during the baseline period prior to the cohort entry date. Differences in the confounder distributions will be inspected for successful confounder balance of measured characteristics and standardized differences will be reported.

9.7.1.2 Rates and Risks

● *Rate of Triple Therapy Initiation*

Among the unmatched and matched cohorts, rates of triple therapy use for each treatment group will be reported as the number of events (first per patient) divided by the total number of person-years at risk during follow-up. Comparative rates and corresponding 95% CIs will be reported as both the rate ratio and rate difference per 1,000 person-years at risk.

● *Risk of Triple Therapy Initiation*

Among the unmatched and matched cohorts, risk of triple therapy use for each treatment group will be reported as the number of events (first per patient) divided by the total number of patients at risk. Comparative risks and corresponding 95% CIs will be reported as both the risk ratio and risk difference per 1,000 person at risk.

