Data analysis:	
 ● Descriptive analyses 
For demographic and lifestyle variables, the value recorded on the cohort entry date will be reported, otherwise the most recent known value will be reported. Presence of comorbidities and use of concomitant medication use will be determined based on whether they ever occurred within the 180-day baseline period preceding the index date. Differences in the confounder distributions will be inspected for successful confounder balance of measured characteristics.
 ● Rate of Triple Therapy Initiation 
Among the unmatched and matched cohorts, rates of triple therapy use for each treatment group will be reported as the number of events (first per patient) divided by the total number of person-years at risk during follow-up. Comparative rates and corresponding 95% CIs will be reported as both the rate ratio and rate difference per 1,000 person-years at risk.
 ● Risk of Triple Therapy Initiation 
Among the unmatched and matched cohorts, risk of triple therapy use for each treatment group will be reported as the number of events (first per patient) divided by the total number of patients at risk. Comparative risks and corresponding 95% CIs will be reported as both the risk ratio and risk difference per 1,000 person at risk.
 ● Comparative Effectiveness ● Hazard Ratio for Triple Therapy Use Initiation 
Among both the basic propensity score matched and high dimensional
		

Name of company: Boehringer Ingelheim			
Name of finished medicinal product: Spiolto® Respimat®; Spiriva® Respimat®			
Name of active ingredient: Tiotropium / Olodaterol fixed dose combination (ATC R03AL06); Tiotropium (ATC R03BB04)			
Protocol date: 27 Feb 2020	Study number: 1237.100	Version/Revision: 1.0	Version/Revision date: N/A

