9.2 SETTING

9.2.1 Definitions

Study Period: the entire period of time that includes the baseline period, the cohort entry date (index date), and follow-up period for the study population. The study period will be from **01 April 2015** (180 days prior to Spiolto approval date of 28 September 2015 in Japan) to **31 March 2019** (end of available data).

Patient Selection Period: the period of time for which patients are eligible to enter the cohort. The earliest date of the patient selection period is **28 September 2015**, (the Spiolto approval date in Japan). The latest date of the patient selection period is 31 December 2018, corresponding to 90 days before the end of available data (31 March 2019), ensuring that all patients have at least 60 days after the cohort entry date to identify a second prescription for index therapy and at least 30 days to be capable of the 30-day overlap to determine the triple therapy initiation outcome.

Cohort Entry Date: Date of entry to the initial cohort of Tio/Olo vs. Tio users (*first prescription*).

Baseline Period: the 180-day period that ends 1 day prior to the cohort entry date used to assess covariate information. The earliest start of the baseline period would be 01 April 2015, corresponding to 180 days prior to the approval date of Spiolto.

[figure not shown]
Follow-Up Period: the period starting at the second prescription for Tio/Olo or Tio within 60 days of the cohort entry date (first prescription) and ending at the earliest occurrence of the outcome (use of triple therapy), or the first occurrence of inpatient death, disenrollment, or end of the study period (31-Mar-2019). A sensitivity analysis will employ an as-treated censoring approach to further censor upon discontinuation of index therapy or initiation of the other index treatment arm. Patients may have different lengths of follow-up (i.e. variable follow-up).

Since health care is nationalized in Japan, the notion of enrollment is not applicable. Therefore, a proxy enrolment criterion defined as start of enrolment = date of first inpatient/outpatient encounter; end of enrolment = date of last inpatient/outpatient encounter will be used. “Enrolment” herein will refer to this proxy enrolment measure. For entry into the study population, patients will be required to have had at least 180 days of enrollment prior to the cohort entry date.

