Data during the baseline period will be used to confirm study eligibility and classification of exposure. The follow-up period will be used for identifying the outcome. This is illustrated in [Figure 1](#).

Figure 1

Study timeline

*Patients are allowed to enter the cohort between 28-September-2015 and 31-December-2018. The last allowable date for start of follow-up is 1-March-2019. The follow-up ends at the earliest occurrence of the outcome, or the first occurrence of inpatient death, disenrollment, or end of the study period (31-Mar-2019). A sensitivity analysis will employ an as-treated censoring approach to further censor upon discontinuation of index therapy or initiation of the other index treatment arm.

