Basic propensity score will be used to assess comparative effectiveness between the two exposure groups. The basic propensity score will be estimated using logistic regression with Tio/Olo treatment as the outcome and the following variables determined *a priori* as predictors:

a) predefined demographic variables (measured at time of cohort entry):

- Age
- Sex
- Calendar Year of Index
- Hospital Size (as a proxy for urban/rural)

b) all concomitant medications and comorbidities/conditions/other variables enumerated in [Section 9.3.3.](#)

The final basic propensity score will then be used to identify one initiator of *Tiotropium* for each initiator of *Tiotropium/Olodaterol* with the same propensity score (\pm a caliper of 5%) (**Austin 2011**).

High Dimensional Propensity Score Matching

In addition to the basic propensity scores, high dimensional propensity score (hdPS) analysis will also be used to assess comparative effectiveness between the two exposure comparison groups. hdPS is a modification of traditional propensity scores that incorporate additional steps for empirical variable selection. Briefly, hdPS includes additional covariates by ranking a complete list of available variables of a given attribute (e.g. all ICD-10 codes) based on prevalence, recurrence, association between covariate and exposure, and association between covariate and outcome, and then including the top covariates in that list in the propensity score prediction. This technique has been shown to produce improved effect estimates compared to using all predefined covariates in the propensity score prediction (**Schneeweiss 2009**).

The set of covariates to estimate the propensity scores will include the same predefined covariates as in the basic propensity scores (categories a and b), but also an empirically chosen set of covariates (category c):

a) predefined demographic variables (measured at time of cohort entry):

- Age
- Sex
- Calendar Year of the Cohort Entry Date
- Hospital Size (as a proxy for urban/rural)

b) all concomitant medications and comorbidities/conditions/other variables enumerated in [Section 9.3.3.](#)

c) The top variables (number of variables determined by the [REDACTED]) chosen by the hdPS algorithm described above. The following attributes will be used to select variables eligible for hdPS analysis:

- Disease Data – ICD-10 Codes
- Inpatient ACT – Health Claim Code
- Outpatient ACT – Health Claim Code
- Lab Data – Laboratory Code

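### The risk of triple therapy is events divided by patients under variable, censored follow-up, so the planned risk difference belongs to no stated time

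*Combined protocol and SAP*

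**What the plan says.** Section 9.7.1.2 sets each group's risk equal to the "number of events (first per patient) divided by the total number of patients at risk", for the unmatched and the matched cohorts. It continues: "Comparative risks and corresponding 95% CIs will be reported as both the risk ratio and risk difference per 1,000 person at risk". The abstract repeats the definition under Data analysis. Neither place attaches a time point, and no Kaplan-Meier or cumulative incidence estimate appears elsewhere in the plan.

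Section 9.2.1 states: "Patients may have different lengths of follow-up (i.e. variable follow-up)". Follow-up starts at the second prescription and ends at triple therapy, inpatient death, disenrollment or 31 March 2019. Disenrollment is a proxy: "end of enrolment = date of last inpatient/outpatient encounter will be used". The note to Figure 1 adds: "The last allowable date for start of follow-up is 1-March-2019".

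The same section 9.7.1.2 also plans measures that do use follow-up time: "Comparative rates and corresponding 95% CIs will be reported as both the rate ratio and rate difference per 1,000 person-years at risk". Section 9.7.1.3 plans the Cox hazard ratio. The only time horizon in the documents is the sample-size assumption in section 9.5: 6% (Tio/Olo) and 10% (Tio) starting triple therapy within one year.

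**The concern.** A proportion of patients with an event estimates a risk only when everyone is observed for the same time, or when the horizon and the censoring are handled explicitly. Here a patient censored at 30 days adds one to the denominator, exactly like a patient seen event-free for three years. The result mixes risks at many different times.

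The risk difference per 1,000 is the figure that readers will take as the absolute benefit. As defined, part of its size comes from how long patients happened to be observed. It cannot be read as a one-year risk, set against the plan's 6% and 10%, or compared with another study. If follow-up also differed between arms, the risk ratio would be distorted too.

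**Working it through.** **Inputs from the documents.** Entry runs from 28 September 2015 to 31 December 2018 (1,191 possible days) and data end on 31 March 2019 (9.2.1). One-year risks are 6% and 10%, with 1,856 patients in total (9.5). Matching is 1:1 (9.1), so 1,856/2 = 928 per arm.

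**Assumptions, not in the documents.** Constant hazards; uniform entry; follow-up starting 30 days after entry; loss to follow-up L of 0, 0.3 or 1.0 per year, independent of outcome and equal in both arms. Matching is ignored in the standard errors.

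**Range of follow-up.** 28 September 2015 to 31 March 2019 is 1,280 days (3.50 years), less the gap to the second prescription. 1 March to 31 March 2019 is 30 days.

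**Hazards.** The plan states no value for the risk difference, so the starting point is its planning risks. −ln(0.94) = 0.0619 and −ln(0.90) = 0.1054 per year. The ratio is 1.70, as in the abstract (section 9.5 prints 1.73). At one year these return 60 and 100 per 1,000, a difference of −40 and a ratio of 0.60.

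**Step 1: complete, equal follow-up.** The difference is 1,000 × [exp(−0.1054t) − exp(−0.0619t)]:

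| t | Difference per 1,000 |
|---|---|
| 30 days | −3.5 |
| 6 months | −20.9 |
| 1 year | −40.0 |
| 2 years | −73.6 |
| 3.5 years | −113.8 |

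The risk ratio moves only from 0.59 to 0.63.

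**Step 2: the plan's calculation.** Over the entry days, potential follow-up t runs from 0.16 to 3.42 years (mean 1.79); 25.7% of patients have under one year even with no loss. The crude risk is the mean over t of h/(h+L) × [1 − exp(−(h+L)t)]. The equivalent horizon is the complete follow-up time that gives the same difference.

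| Loss per year | Tio/Olo | Tio | Difference per 1,000 | Ratio | Equivalent horizon |
|---|---|---|---|---|---|
| 0 | 10.4% | 16.8% | −64.6 | 0.616 | 1.71 years |
| 0.3 | 7.6% | 12.5% | −48.6 | 0.611 | 1.24 years |
| 1.0 | 4.5% | 7.4% | −29.3 | 0.604 | 0.71 years |

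Starting follow-up 1 or 60 days after entry instead of 30 gives −67 to −62, −50 to −47 and −30 to −29.

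**Step 3: unequal follow-up, illustration only.** Take no treatment effect, 10% per year in both arms, no loss, and potential follow-up between 30 days and 3.50 years: uniform for Tio (mean 1.79 years), linearly decreasing for Tio/Olo (mean 1.22 years). The crude risks are 117.8 and 167.7 per 1,000: a spurious difference of −49.9 and a ratio of 0.70. The documents do not show such an imbalance.

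**Step 4: precision of a fixed horizon.** Crude standard errors are binomial and fixed-time ones use Greenwood's formula, with 928 per arm.

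| Loss per year | Events used by 12 months | SE of log RR, crude → 12 months | SE of difference per 1,000, crude → 12 months |
|---|---|---|---|
| 0 | 53% | 0.121 → 0.174 (+43%) | 15.8 → 13.4 |
| 0.3 | 62% | 0.143 → 0.188 (+31%) | 13.9 → 14.5 |
| 1.0 | 79% | 0.191 → 0.231 (+21%) | 10.9 → 17.8 |

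A simulation of the 12-month Kaplan-Meier estimate (4,000 replicates) gave standard errors of 13.6, 14.7 and 17.8 for the difference, and a mean difference of −40 in all three scenarios.

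At 24 months the difference is −73.6 per 1,000 (11.6% v 19.0%). The SE of the log risk ratio is 0.136, 0.163 and 0.263 (+12%, +14% and +37% on crude), and that of the difference is about 20, 24 and 39 per 1,000.

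**The case against.** The strongest reply is that this is one supportive presentation. Directly above it the plan already gives a time-standardised absolute comparison, the rate difference per 1,000 person-years; under the model used here the rates would be about 62 v 105. The Cox hazard ratio is intact and the risk ratio hardly moves. All of this is right, and it limits the weight of the point. It does not give the planned risk difference a meaning, and a rate is not a risk.

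Second, the losses of 0.3 and 1.0 per year are hypothetical, and they apply only if follow-up ends at the last encounter, as in section 9.2.1. The censoring paragraph of section 9.3.2.1 lists only outcome, death and end of data, and section 9.9 assumes that patients remain observable throughout. On that reading only the zero-loss row applies. It still gives −65 at an unstated horizon of about 1.7 years, because entry dates alone spread follow-up widely.

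Third, index year ("Calendar Year of Index") is in the propensity score. That should limit differences in follow-up between arms after matching, although how far is not shown. It creates no horizon and does nothing for the unmatched cohort.

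Fourth, a fixed horizon costs precision. The smaller standard error of the difference at zero loss is no gain, because the effect shrinks as well: at 12 months the difference divided by its standard error falls from 4.1 to 3.0, 3.5 to 2.8 and 2.7 to 2.2. This stands as a cost.

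**Conclusion.** The concern holds. Followed as written, the plan produces a risk difference tied to no time. On its own planning rates, one treatment effect would be reported as anything from about −65 to −29 per 1,000, depending only on observation time, against −40 at one year. Those figures rest on constant hazards, uniform entry, equal follow-up in both arms and the assumed loss rates; the documents supply none of these. The lack of a horizon depends on none of them.

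The consequence is confined to the absolute risk contrast and, where follow-up differs by arm, the risk ratio. The hazard ratio, the person-year rates and the primary conclusion are unaffected. It should be corrected before outcomes are seen.

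**What to change.** In section 9.7.1.2 and the abstract:

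- Base the risk ratio and the risk difference per 1,000 on the cumulative incidence of triple therapy at one pre-specified time from the start of follow-up, for example 12 months, the horizon of the sample-size assumption.
- Name one estimator in advance: Aalen-Johansen with inpatient death as a competing event, or Kaplan-Meier with death censored as in section 9.3.2.1. State that only inpatient deaths are captured (section 9.9).
- In the matched cohorts, use confidence intervals that respect the matching, such as a bootstrap of matched pairs.
- Keep events over patients only as a descriptive count, labelled *over observed follow-up*, next to median follow-up by arm.
- Apply one end-of-follow-up rule. Sections 9.2.1, 9.3.2.1 and 9.9 differ and must be reconciled; this also affects the rates and the Cox model and is a separate point.

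The cost is a short text change with the same data, plus the loss of precision shown above. A 24-month horizon keeps about 85% to 90% of events at losses of 0 to 0.3 per year and costs the log risk ratio less there, but it is worse than 12 months if loss is near 1.0 per year. Events after the horizon stay in the Cox model and the rates. Either estimator assumes uninformative censoring, which is uncertain if follow-up ends at the last encounter.

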9.7.1.3 Comparative Effectiveness

● *Hazard Ratio for Triple Therapy Use Initiation*

Among both the basic propensity score matched and high dimensional propensity score matched cohort, Cox regression will be used to estimate the hazard ratios and 95% CI for Tiotropium/Olodenaterol compared to patients treated with Tiotropium during follow-up for time-to-first triple therapy initiation using an intention-to-treat censoring approach.

9.7.2 Subgroup analysis

Not applicable.

9.7.3 Sensitivity Analyses

1. Less Stringent Qualifying Event Criterion

Instead of defining the event to qualify patients for inclusion based on two prescriptions within 60 days, patients may enter upon only one prescription. While some confidence is lost in whether the patients truly took their index medications, the less stringent qualifying event criterion will allow more patients to be included, increasing statistical power. Furthermore, the possibility of immortal time bias is also mitigated, since the time between prescriptions is no longer present.

2. As-treated Censoring

The analysis will use an as-treated approach for primary, secondary and further endpoint outcomes. In addition to the censoring criteria mentioned for the intention-to-treat approach (outcome, death, or end of data), patients will also be censored after medication discontinuation or switching over to the other arm.

3. Alternative algorithm for COPD

The analysis will use a different set of diagnosis codes for COPD (J43*, J44*) when selecting COPD patients. Compared to the primary analysis, this algorithm omits the diagnostic code for chronic bronchitis (J41*), as this code is commonly used by pulmonologists when prescribing Mucodyne to patients who do not actually have chronic bronchitis. While some true chronic bronchitis patients may be excluded, the selection of patient will increase specificity.

4. Asthma patients with doubt

Asthma patients with doubt are defined as patients with a diagnosis code for asthma and without evidence of any asthma specific treatment (ie., ICS, ICS/LABA). This sensitivity analysis will include patients identified with asthma with doubt.

5. ACOS sensitivity analysis

Patients that have evidence of asthma during the follow-up period will have their data censored on the date of asthma diagnosis during the follow-up period. This will ensure that they contribute information during their COPD disease trajectory up until the time they develop asthma. This approach will mitigate introducing immortal time bias for those patients with ACOS during the follow-up period.

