
propensity score matched cohort, Cox regression will be used to estimate the hazard ratios and 95% CI for Tiotropium/Olodaterol compared to patients treated with Tiotropium during follow-up for time-to-first triple therapy initiation using an intention-to-treat censoring approach.
 
Sensitivity Analyses
 
 1. Less Stringent Qualifying Event Criterion 
Instead of defining the qualifying event as two prescriptions within 60 days, patients may enter on only one prescription. While some confidence is lost in whether the patients truly took their index medications, the less stringent qualifying event criterion will allow more patients to be included, increasing statistical power. Furthermore, the possibility of immortal time bias is also mitigated, since the time between prescriptions is no longer present.
 
 2. As-treated Censoring 
The analysis will use an as-treated approach for primary, secondary and further endpoint outcomes. In addition to the censoring criteria mentioned for the intention-to-treat approach (outcome, death, or end of data), patients will also be censored after medication discontinuation or switching over to the other arm.
 
 3. Alternative algorithm for COPD as exclusion criterion 
The analysis will use a different set of diagnosis codes for COPD (J43*, J44*) to identify patients with COPD. Compared to the primary analysis, this identification approach omits the diagnostic code for chronic bronchitis (J41*), as this code is commonly used by pulmonologists when prescribing Mucolytics to patients without
			

Name of company: Boehringer Ingelheim			
Name of finished medicinal product: Spiolto® Respimat®; Spiriva® Respimat®			
Name of active ingredient: Tiotropium / Olodaterol fixed dose combination (ATC R03AL06); Tiotropium (ATC R03BB04)			
Protocol date: 27 Feb 2020	Study number: 1237.100	Version/Revision: 1.0	Version/Revision date: N/A

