9.2.2 Study population

The study cohort will include all patients who initiate Tiotropium/Olodaterol (Tio/Olo) or Tiotropium (Tio) during the patient selection period. Initiation (new use) will be determined based on no prescription claims for Tio/Olo or Tio during the baseline period or during all available data prior to cohort entry date. All patients will additionally be required to have a second claim for the index medication within 60 days after cohort entry to ensure primary adherence of index therapy.

The following exclusion criteria will then be applied to generate the unmatched cohort:

- Aged <40 years on cohort entry.

[figure not shown]
Proprietary confidential information © 2020 Boehringer Ingelheim International GmbH or one or more of its affiliated companies

- Any LAMA, LABA, ICS maintenance therapy (alone or in combination) during the 180-day baseline period prior to cohort entry for maintenance treatment and not cough, i.e. duration >30 days, or any prescription within the 30 days prior to cohort entry.
- Patients without continuous enrolment (days since first inpatient/outpatient encounter in the data) during the baseline period.
- No prior diagnosis of COPD [ICD-10: J41*, J43*, J44* and doubt (UTAGAIFLG) = 0 (no)]
- Patients without a second prescription claim of their index medication within 60 days after the cohort entry date.
- Diagnosis of asthma [ICD-10: J45* and doubt (UTAGAIFLG) = 0 (no)] during the baseline period.
- Diagnosis of lung cancer [ICD-10: C34*, D02.2, Z80.1, Z85.1 and doubt (UTALAIFLG) = 0 (no)] or lung transplant (Health claim code: 150317670, 150322510, 150322610, 150336510, 150336610, 150336710, 150399270) prior to the cohort entry date using all available data.
- Patients who initiate both Tio/Olo and Tio simultaneously on the cohort entry date.
- Any use of triple therapy (LAMA + LABA + ICS) during the baseline period or between the cohort entry date and 1 day prior to the start of follow-up.

All patients will be selected into the first treatment arm (Tio/Olo or Tio) that they qualify for and will not be allowed to re-enter the cohort by design.

The cohort will then be used to construct two matched cohorts (not mutually exclusive) according to the: 1) basic propensity scores and 2) high dimensional propensity scores

Figure 2 Depicts the flow diagram of patients.

Basic Propensity Score Matching

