9.12 BIAS

In principle, electronic pharmacy dispensing records are considered accurate because pharmacists fill prescriptions with little room for interpretation, and are reimbursed by insurers based on detailed, complete, and accurate claims submitted electronically (Levy 2003; Sternbach 1988). Pharmacy dispensing information is usually seen as the gold standard of drug exposure information compared to self-reported information or prescribing records in medical records.

The population-based nature of the database will avoid selection bias and ensure external validity. Confounding bias through observable covariates will be controlled for by the design, which includes propensity score matching. Specifically, compared to traditional propensity

score matching, high dimensional propensity scores will be used to reduce overfitting while retaining baseline covariate balance in matched groups (**Schneeweiss 2009**).

To minimize misclassification of the recorded patient characteristics, previously validated algorithms or code lists will be used whenever available. Code lists will be reviewed by the qualified medical reviewers prior to implementation. Basic plausibility checks will be implemented for continuous variables (e.g. age, etc.).

The covariates chosen in [section 9.3.3](#) are hypothesized to be confounders in the relationship between exposure and outcome. The range and quantity of variables selected are aimed to make the two exposure groups more comparable so that the effect estimates may more readily have a causal interpretation.

COPD patients who start on Spiriva® Respimat® may be different than Spiolto® Respimat® initiators in the clinical course and severity of COPD. Use of propensity score matching aim to reduce bias due to confounding. The addition of covariates chosen by hDPS will further aid in reducing bias by empirically selecting for strong confounders. However, it is possible that inclusion of some variables may introduce rather than remove bias (i.e. as collider bias or M-bias). Nevertheless, such biases are demonstrated to be minor, and inclusion of variables preceding exposure are generally thought to improve rather than degrade validity (**Rassen 2011**).

The requirement of second fill for inclusion in the study could lead to immortal time bias. However, as the follow-up will begin after the second fill rather than at the cohort entry date, this requirement is unlikely to bias the findings.

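### Sensitivity analysis 1 does not restate the start of follow-up, and under the plan's own rule patients who begin triple therapy on the entry date are no longer excluded and can count as time-0 events

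*Combined protocol and SAP*

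**What the plan says.** - **Start of follow-up, main analysis.** Section 9.2.1 defines follow-up as "the period starting at the second prescription for Tio/Olo or Tio within 60 days of the cohort entry date (first prescription". The note to Figure 1 gives 1 March 2019 as the last possible start.
- **Triple-therapy exclusion.** Section 9.2.2 excludes any triple therapy in the baseline period or "between the cohort entry date and 1 day prior to the start of follow-up". Section 9.2.1 defines baseline as "the 180-day period that ends 1 day prior to the cohort entry date".
- **SA1.** Section 9.7.3 says "patients may enter upon only one prescription", and the abstract says "patients may enter on only one prescription". Section 9.7.3 adds that "the possibility of immortal time bias is also mitigated, since the time between prescriptions is no longer present". Neither place gives SA1's start of follow-up or says how the exclusion applies to it.
- **Outcome.** Section 9.3.2.1 counts a triple fixed-dose combination, or 30 consecutive days of concurrent use of the components. It assumes 30 days' supply and dates the event at the first day of overlap.
- **Bias section.** Section 9.12 words the start of follow-up differently: "as the follow-up will begin after the second fill rather than at the cohort entry date".

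**The concern.** The post-entry part of the exclusion is tied to the start of follow-up. In the main analysis there is a gap between first and second prescription, so that part has days in it and removes anyone who begins triple therapy on the entry date. SA1 takes the gap away, and the part of the exclusion that depended on it goes too.

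SA1 is the one analysis that tests the second-prescription rule. If it also admits patients who were on triple therapy from the first day and counts them as escalating, a difference between SA1 and the main result can no longer be put down to that rule alone. These patients never had a period on Tio or Tio/Olo from which to escalate.

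**Working it through.** **1. When SA1 follow-up starts.** This is inferred, because the plan does not write it. The formal definition in 9.2.1 starts follow-up at the qualifying prescription. The plan's calendar agrees: last entry 31 December 2018 + 60 days = 1 March 2019, the date in the note to Figure 1. Starting the day after the second prescription would give 2 March 2019. With one qualifying prescription, the same rule puts the start on the cohort entry date (day 0). This also fits SA1's statement that no time between prescriptions remains.

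**2. The post-entry exclusion window.** It runs from day 0 to (start of follow-up - 1).

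| Case | Start | Window | Day 0 covered? |
|---|---|---|---|
| Main analysis, second prescription on day 30 (example) | 30 | days 0 to 29 | yes |
| SA1, start at the single prescription | 0 | day 0 to day -1, empty | no |
| SA1, start the day after the prescription | 1 | day 0 only | yes |

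**3. Other criteria that might cover day 0.** The baseline part ends on day -1. The LAMA/LABA/ICS washout looks back only; its shorter limb is "any prescription within the 30 days prior to cohort entry". The same-day exclusion concerns only Tio/Olo together with Tio. None covers an ICS or LABA/ICS first prescribed on day 0.

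**4. Whether such a patient has an event.** A triple fixed-dose combination counts at once. For separate products with 30 days' supply each, co-prescription on day 0 meets the 30-day overlap and the event is dated day 0.

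**5. Illustrative size.** The plan has no figure for day-0 triple starts, so the share u is an assumption.
- Inputs from section 9.5: one-year risks p of 10% (Tio) and 6% (Tio/Olo).
- Base HR, Tio/Olo against Tio: ln(0.94)/ln(0.90) = 0.587. Its reciprocal, 1.703, matches the abstract's 1.7 (section 9.5 prints 1.73).
- Apparent one-year risk = u + (1 - u)p. Approximate HR = ln(1 - risk Tio/Olo)/ln(1 - risk Tio).
- Example, u = 5% in both arms: Tio/Olo 0.05 + 0.95 × 0.06 = 0.107; Tio 0.05 + 0.95 × 0.10 = 0.145.

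| u Tio | u Tio/Olo | Risk Tio | Risk Tio/Olo | Risk ratio | Approx. HR | Cox HR, simulated |
|---|---|---|---|---|---|---|
| 0 | 0 | 0.100 | 0.060 | 0.60 | 0.587 | 0.59 |
| 1% | 1% | 0.109 | 0.069 | 0.64 | 0.623 | 0.62 |
| 5% | 5% | 0.145 | 0.107 | 0.74 | 0.722 | 0.73 |
| 5% | 1% | 0.145 | 0.069 | 0.48 | 0.459 | 0.46 |
| 1% | 5% | 0.109 | 0.107 | 0.98 | 0.981 | 1.00 |

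The simulation used 200,000 patients per arm, one year of follow-up and Efron ties, with time-0 events kept in the risk set. Longer follow-up dilutes the effect. With follow-up spread evenly over 0.25 to 3.5 years and no early disenrolment, 5% on Tio against 1% on Tio/Olo gives about 0.50 instead of 0.46.

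**The case against.** The strongest reply is that the plan never says SA1 follow-up starts on day 0. Section 9.12 puts the start after the fill; carried over to the single prescription, that means day 1, and day 0 stays inside the exclusion. It stands that the day-0 start is an inference. But 9.12 is narrative, while the definition in 9.2.1 and the 1 March 2019 date both put the start on the prescription date. Either way, the sections disagree and SA1 depends on which is followed.

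The overlap is also not automatic. Sections 9.3.1 and 9.6 assign 14 days to the Spiolto 28-puff pack, although 9.3.1 lists the same pack at 30 days and 9.3.2.1 assumes 30 days for the outcome. At 14 days, one such pack plus an ICS overlaps for only 14 days and needs a refill to count. This stands: not every day-0 starter becomes an event, and capture may differ by arm.

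Dropping the second-prescription rule must in any case move time zero and count triple starts between day 1 and the second prescription. That change belongs to SA1. A reader might infer that SA1 cannot be compared with the main analysis at all. The documents do not support that; only the day-0 component is avoidable.

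**Conclusion.** The point holds for SA1. Applied under the plan's own start rule, SA1 keeps patients who begin LAMA, LABA and ICS on the entry date and counts those who meet the outcome definition as events at time 0, although the main analysis removes them.

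Two stronger readings are tempting and not supported. One is that the primary result is affected. It is not, because the main analysis has a non-empty window that covers day 0; the 180-day baseline part also remains in force in SA1. The other is that the error favours Tio/Olo. The documents give no day-0 share for either arm. Equal shares pull the HR towards 1 (0.62 to 0.73 for 1% to 5%), and unequal shares can move it either way (0.46 or about 1.00).

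These sizes rest on assumed shares, the plan's 10% and 6% risks, one-year follow-up and all day-0 starters counting as events. The plan does not say how time-0 events enter the Cox model, but the crude risks in 9.7.1.2 would count them.

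**What to change.** In section 9.7.3 and in the abstract:
1. State that SA1 excludes patients whose triple therapy (LAMA, LABA and ICS) starts on the cohort entry date.
2. Start SA1 follow-up on the day after entry.
3. Report the number excluded for this reason, by arm.

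Also reconcile the start of follow-up in 9.2.1 with the wording in 9.12, and the two days-supply values that 9.3.1 gives for the Spiolto 28-puff pack.

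The cost is one sentence in each place and one programming condition. SA1 loses a few patients, all of whom the main analysis already excludes.
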